Caregivers will complete a baseline survey using a REDCap link that will be delivered to caregivers via email or text message. The survey will include sociodemographic characteristics and the outcome measures (i.e., Revised Memory and Problem Behavior Checklist and Preparedness for Caregiving Scale). We will collect outcome measures from caregivers again 6-8 weeks post-enrollment using the same data collection method. Sociodemographic characteristics will include: caregiver age, occupational status, whether caregiver works outside of the home, number of people living in caregiver’s home, educational attainment, English fluency, preferred language, languages spoken at home, race, gender, annual household income, device ownership, Internet access at home, health insurance status of caregiver and PLWD, relationship to PLWD, age of PLWD, gender of PLWD, number of years in caregiving role, whether caregiver lives in same household as PLWD, and hours per week providing care.

After completing the baseline survey, caregivers will begin participation in the intervention. ***The intervention tested in this study will only involve the self-directed training component of the STAR-VTF intervention.*** We will provide caregivers with the video modules via text message or email. We will also mail each participant a copy of the adapted version of the STAR-VTF workbook in their preferred language. There are handouts and resources to along with each lesson. Caregivers will be instructed to complete 1 module per week for 7 weeks (Table 2).

After 6-8 weeks, we will schedule an exit interview with caregivers. The interview will happen virtually (phone or videoconferencing) and will be under 1 hour. We will ask participants semi-structured questions to understand their experience with the online training modules and with completing the survey via REDCap.

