6.2.3 Module Assessment

At the end of each online training module, there is a short survey that caregivers are asked to complete. The survey contains:

- System Usability Scale

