6.2.4 Final Assessment

After 6-8 weeks post-enrollment, caregivers will receive an email or text message asking them to complete the REDCap baseline survey that contains:

- Revised Memory and Problem Behavior Checklist
- Preparedness for Caregiving Scale

In addition, study staff members will schedule an exit interview with participants. The interview will happen virtually (phone or videoconferencing) and will be under 1 hour. We will ask participants semi-structured questions to gauge their acceptance of the online learning modules and their experience completing the REDCap survey.

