7.2 Adverse Event (AE) and Serious Adverse Event (SAE) Collection and Reporting

7.2.1 AE/SAE Definitions

The study will adhere to the definitions for AEs and SAEs stipulated in the [NIA Adverse Event and Serious Adverse Event Guidelines](#) as outlined below.

AE Definition: AE is any untoward or unfavorable medical occurrence in a human study participant, including increased stressed, inability to cope, or other emotional discomfort, temporally associated with the participants' involvement in the research, whether or not considered related to participation in the research.

AEs for this study include:

This study is designed to pilot test a behavioral intervention with caregivers. As such, we believe it will pose minimal risk to participants because the probability and magnitude of harm or discomfort anticipated are not greater in and of themselves than those ordinarily encountered in daily life or during the performance of routine physical or psychological examinations or tests. The risks of participating in this study may include feeling discomfort discussing personal matters during the intervention, survey, or exit interview, as well as frustration as caregivers attempt to implement the suggestions of the STAR-VTF online learning modules.

SAE Definition: SAEs consist of any adverse event that results in death; is life threatening or places the participant at immediate risk of death from the event as it occurred; requires or prolongs hospitalization; causes persistent or significant disability or incapacity; results in congenital anomalies or birth defects; is another condition which investigators judge to represent significant hazards

SAEs for this study include:

Research activities may identify immediate risk of harm or other urgent need. While we would not conclude that any such emergencies are consequences of study participation or

intervention content, there is still a clear obligation to report and respond appropriately to these urgent needs.

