7.2.3 AE/SAE Reporting

The study will adhere to the reporting requirements for AEs and SAEs stipulated in the [NIA Adverse Event and Serious Adverse Event Guidelines](#) as outlined below.

Process for identifying AEs and SAEs: The study staff members, [name] and [name], will be in contact with participants while carrying out research activities and will be able to identify any AEs and SAEs that occur. When an adverse event is identified, [name] and study staff will follow [NIA's AE/SAE process flow](#). They will meet on a weekly basis throughout the project period and will review study progress and adverse events. NIA's [template for AEs](#) and [template for SAEs](#) will be used to collect information about adverse events.

Adverse event reporting schedule:

- All **adverse events that are both serious (SAE) and unexpected** (i.e., have not been previously reported for the study's intervention) will be reported to the IMPACT Collaboratory Regulatory and Data Team Leader ([name] PhD), Advarra IRB, NIA IMPACT Collaboratory PO ([name]), and the IMPACT Collaboratory DSMB Chair (or the project's Safety Officer) within 48 hours of the study's knowledge of SAE.
- The summary of all other SAEs will be reported to IMPACT Collaboratory Regulatory and Data Team Leader ([name] PhD), Advarra IRB, NIA IMPACT Collaboratory PO ([name]), and the IMPACT Collaboratory DSMB Chair (or the project's Safety Officer) quarterly, unless otherwise requested by the DSMB Chair or a Safety Officer.
- All deaths will be reported to IMPACT Collaboratory Regulatory and Data Team Leader ([name] PhD), Advarra IRB, NIA IMPACT Collaboratory PO ([name]), and the IMPACT Collaboratory DSMB Chair (or the project's Safety Officer) and to the DSMB Chair (or project's Safety Officer) within 24 hours of study's knowledge of death.
- AEs will be reported per IRB policies and also to IMPACT Collaboratory Regulatory and Data Team Leader ([name] PhD), Advarra IRB, NIA IMPACT Collaboratory PO ([name]), and the IMPACT Collaboratory DSMB Chair (or the project's Safety Officer) and to the DSMB Chair (or project's Safety Officer) at minimum every 6 months, or at a frequency requested by NIA and/or by the DSMB.

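### Section 7.2.3 says staff contact will identify every adverse event, but no two-way contact is scheduled between consent and the exit interview and no participant survey asks about adverse events

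*Combined protocol and SAP*

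**What the plan says.** Section 7.2.3 gives one way of finding adverse events: study staff "will be in contact with participants while carrying out research activities and will be able to identify any AEs and SAEs that occur". NIA templates for AEs and SAEs "will be used to collect information about adverse events". The investigator and staff have a regular internal review: "They will meet on a weekly basis throughout the project period and will review study progress and adverse events".

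The definition in 7.2.1 is broad. It covers unfavourable occurrences "including increased stressed, inability to cope, or other emotional discomfort, temporally associated with the participants' involvement in the research". Among the risks that the section anticipates is "frustration as caregivers attempt to implement the suggestions of the STAR-VTF online learning modules".

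The delivery model involves little contact. Section 3 states: "The intervention tested in this study will only involve the self-directed training component of the STAR-VTF intervention". Sections 2.2 and 5.1 confirm that coaching is left for a later study. On data collection, 6.2.3 says: "At the end of each online training module, there is a short survey that caregivers are asked to complete". It lists the System Usability Scale as the content. The final survey in 6.2.4 holds the Revised Memory and Behavior Problem Checklist and the Preparedness for Caregiving Scale. The exit interview uses "semi-structured questions to gauge their acceptance of the online learning modules and their experience completing the REDCap survey".

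**The concern.** The statement in 7.2.3 is a claim of complete ascertainment, and it rests entirely on staff being in contact with caregivers. In this pilot the modules are done alone, at home, over several weeks. The events the protocol names (stress, difficulty coping, frustration when trying out the suggestions) are most likely to arise in those weeks. They are also events that staff seldom learn of unless they ask.

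Two things are at stake. The first is timeliness. The 24-hour clock for deaths and the 48-hour clock for serious unexpected events both start when the study learns of the event, so an event that nobody volunteers may not start a clock until the exit interview. The second is interpretation. If few or no events are recorded, the count cannot be read as evidence about harm without knowing how events were sought, and the protocol as written would lead a reader to think that capture was complete.

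**Working it through.** The plan gives no adverse event rate or detection rate, so there is no figure to reproduce. The check sets the claim in 7.2.3 against the scheduled procedures.

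**Step 1. Scheduled two-way contact (4.3, 6.2.1, 3, 6.2.4)**
- Week 0: a screening call, then a call to go through the consent form.
- After 6-8 weeks: the exit interview, by phone or video.
- In between: modules and survey links sent by email or text. No call or visit is scheduled.

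The gap from the consent call to the interview is about 6 × 7 = 42 to 8 × 7 = 56 days.

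**Step 2. What caregivers are asked**

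| Point of collection | Content | Adverse event question? |
|---|---|---|
| Schedule, 6.1 | No adverse event row in any column; Weeks 1-6 list usability only | No |
| Baseline survey, 6.2.2 | Sociodemographics and the two scales | No |
| Module-end survey, 6.2.3 and appendix | Ten usability items; the open field is for comments on the website | No |
| Final survey, 6.2.4 | The two scales | No |
| Exit interview, 3 and 6.2.4 | Experience and acceptance of the modules; survey experience | Not listed; guide still to be developed (9.4.2) |

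The two scales come near the subject without covering it. The checklist asks how much each behaviour of the person with dementia bothered the caregiver, and only for the past week. The preparedness scale asks how ready the caregiver feels for the stress of caregiving. Neither asks whether an adverse event has happened to the caregiver since the last contact.

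**Step 3. Staff-side procedures**
- The NIA templates are named for recording information on events. Nothing says that their content is put to caregivers on a schedule.
- The weekly meeting in 7.2.3 is among the investigator and staff.
- The log in 10.3.3, also reviewed weekly, tracks survey prompts and interview scheduling, not events.

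**Step 4. Routes that remain**
- Unprompted recall at the exit interview.
- The documented reason for discontinuation (section 8), for caregivers who withdraw.
- Spontaneous messages, for example a reply to an email or text.

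**Step 5. Illustration of what a zero count would mean**

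Inputs: n = 20, the maximum in 9.2; capture probability c, which is an assumption because the documents give none. With zero recorded events, the one-sided 95% upper bound on the true proportion of caregivers with an event is

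(1 − 0.05^(1/n)) / c

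- c = 1: 1 − 0.05^(1/20) = 0.139, or 13.9%.
- c = 0.5: 0.139 / 0.5 = 0.278, or about 28%.

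The sample may be smaller. Section 9.3 stops the study only if fewer than 5 are recruited. With n = 5 the bounds are 45.1% (c = 1) and 90.1% (c = 0.5).

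**The case against.** The strongest reply is that the study is small, educational and judged minimal risk (5.1, 7.1, 7.2.1), and that every caregiver is to be invited to a one-to-one interview of up to an hour. Section 3 describes that interview as covering the experience with the modules, which is a natural place for frustration or discomfort to come up. Section 8 documents why people discontinue and continues follow-up with permission. Email and text messages allow replies. The pilot does not aim to estimate an adverse event rate, and AEs are not among its outcomes in 9.4.

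Much of this stands, and it rules out several stronger readings that a reader might infer:

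- *That harms in the module weeks are largely undetectable, or that the event count would be clean by construction.* The routes above are real, though partial. Unsolicited, late and probably under-counted is as far as the documents go.
- *That no contact can fall in any of the seven module weeks.* Modules run one per week for 7 weeks and the interview window opens after 6, so the interview may overlap the last module.
- *That survey links are automated and one-way.* The documents say only that they go by email or text.
- *That the reporting clocks are faulty.* Running them from the study's knowledge is a reporting rule. The weakness lies upstream, in how the study comes to know.
- *That caregivers receive no instructions for reporting problems.* The consent pages were not available and the NIA process documents are only linked, so this cannot be said.

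What does not stand is the inference that the sentence in 7.2.3 is therefore adequate. Reporting instructions, if they exist, would produce spontaneous reports, which do not amount to identifying every event. A caregiver who stops silently without withdrawing and misses the interview falls outside both the interview and the discontinuation record. Minimal risk justifies a light method of asking. It does not justify claiming complete ascertainment without one.

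**Conclusion.** The point holds in a limited form. The claim of complete identification in 7.2.3 is not supported by the procedures in the visible protocol: no two-way contact is scheduled for about 42 to 56 days, 6.1 has no adverse event row, and no participant-facing survey contains an adverse event question. Events as defined in 7.2.1 would reach the study through spontaneous report, a stated reason for withdrawal, or unprompted recall at the interview.

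This conclusion rests on the text of the procedures and does not depend on the illustrative bounds. The 13.9% figure assumes 20 caregivers followed with full capture. The figure of about 28% adds the assumption that half of events are captured, which has no source in the documents. Confidence is limited by the unseen consent pages and the interview guide that is still to be written. The change is worth making before enrolment because it is cheap and gives the event count a stated method.

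**What to change.** 1. Write one fixed question, for example: since the last survey, have you had more stress, trouble coping, a health problem or a hospital visit? Put it in the final REDCap survey, the exit interview guide and the module-end survey. The first two are needed because the module-end survey reaches only caregivers who finish a module.
2. First reconcile where the module-end survey sits. Sections 6.2.3 and 9.4.2 place it in the modules, while 10.1 describes a REDCap link. The answer decides who can edit the form and whether staff can see responses week by week.
3. Add an adverse event row to the schedule in 6.1.
4. Review the answers at the weekly meeting already planned in 7.2.3.
5. Replace the sentence claiming that every event will be identified with a description of this method, so that any event count is reported together with how events were sought.

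A phone call to caregivers who go quiet is not needed for this change. It could act as a reminder and so affect adherence, which is a secondary outcome (5.4, 9.4.2). If the team wants such calls, they should be logged and reported alongside adherence.

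The cost is protocol wording, one survey item, a few seconds per survey for caregivers and a small amount of staff review. If the module-end survey is embedded in the learning management system, there is also the work of editing it there and arranging weekly access to the answers.

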8 INTERVENTION DISCONTINUATION

The intervention will be discontinued if they withdraw from participation in the study at any time and for any reason. We will document reason for discontinuation and, with their

permission, we will continue to follow-up with participants. We will replace participants who discontinue early (i.e., at enrollment).

9 STATISTICAL CONSIDERATIONS

9.1 General Design Issues

The overall objective of this pilot study is to prepare the culturally and linguistically adapted online training modules for Latino caregivers of PLWD and the REDCap survey that will be used to pragmatically collect caregiver outcomes in a future study. Thus, the study was not designed to test hypotheses. We have selected outcome measures that have already been translated and validated in Spanish: (1) Revised Memory and Behavior Problem Checklist^{27,28} and (2) Preparedness for Caregiving Scale.²⁹

9.2 Sample Size and Randomization

This study does not involve randomization. We have selected a sample size of up to 20 caregivers for study participation for pragmatic reasons (i.e., what can feasibly be accomplished given the study budget and timeline).

9.3 Interim analyses and Stopping Rules

We are not planning to conduct an interim analysis. Given the small sample of the pilot study, it is not possible to detect a significant positive or negative effect of the intervention to terminate recruitment early. Thus, we believe that a decision to prematurely terminate study recruitment or study intervention is not possible.

We have allocated 4 months of our 12-month study to recruiting study participants. If we are unable to recruit at least 5 study participants during that 4-month period, we will stop the study due to slow accrual.

9.4 Outcomes

9.4.1 Primary outcome

The primary outcomes are: (1) Revised Memory and Behavior Problem Checklist and (2) Preparedness for Caregiving Scale. We will collect these outcomes at baseline and 6-8 weeks post-enrollment via a REDCap survey.

- 1. Revised Memory and Behavior Problem Checklist.**^{27,28} Caregivers will rate memory, depression, and disruptive behavior problems in the PLWD. The instrument contains 24 items (7 memory-related, 8 depressive, and 9 disruptive) that assess problem behaviors and are rated for frequency of occurrence during the past week and caregiver reaction to the problem behaviors.
- 2. Preparedness for Caregiving Scale.**²⁹ Caregivers will rate how prepared they are for various aspects of caregiving. The instrument contains 8 items that ask caregivers how well prepared they believe they are to provide physical care, emotional support, deal with the stress of caregiving, and set up in-home support services. Each item is rated on a 5-point scale ranging from 0 (not at all prepared) to 5 (very well prepared).

9.5 Data Analyses

For analysis of quantitative outcomes, we will use descriptive statistics. For qualitative outcomes, we will use analytic procedures in qualitative research.³¹ Given the small sample size and study objectives, we will not perform subgroup analyses.

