qualitative interviews 6-8 weeks post-enrollment. The interviews will assess caregiver satisfaction with and acceptability of the adapted online training modules.

Interventions and Duration

For 6-8 weeks, caregivers will complete online training modules asynchronously. They will access the modules via email or text message. There are 7 online training modules. Caregivers will be instructed to complete one module per week. The content of the modules is as follows: Module 1 provides an understanding and overview of dementia; Module 2 introduces caregivers to the behavioral treatment of dementia, realistic expectations, and effective communication; Module 3 covers the ABC (antecedents, behaviors, consequences) approach to problem-solving, including rationale and development of an ABC plan; Module 4 instructs caregivers to review the ABC plan and revise as needed; Module 5 covers pleasant events and managing negative thinking; Module 6 instructs caregivers to review the ABC plan, pleasant activities schedule, and to revise as needed; Module 7 covers coping with caregiving and maintaining gains. Each module takes about 15 minutes to complete. The modules use text, pictures, and illustrations with a voiceover presentation. Caregivers will receive the online training modules in their preferred language (English or Spanish). They will also receive a workbook to accompany the lessons. The total length of time each caregiver will be in the study is approximately 8 weeks.

Sample Size and Population

Participants will: be aged 18 years or older, live with PLWD or within 5 miles, provide at least 8 hours of care per week, provide care to PLWD who lives at home, and self-identify as Hispanic/Latino. We expect to enroll up to 20 participants. The primary objective of this study is to pilot test the adapted online training modules. Therefore, it is not powered to detect an effect of the intervention.

STUDY TEAM ROSTER

Principal Investigator: [name], MS, MS

Hans Rosling Center for Population Health: Department of Health Services
[name]
[name]
[name]
[contact]
[contact]

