1.2 Secondary Objectives

The objectives of this study are to: (1) culturally and linguistically adapt the STAR-VTF online training modules for Latino caregivers of PLWD, (2) pilot test Latino caregivers' responses to the adapted online training modules, and (3) develop a REDCap survey to pragmatically collected caregiver outcomes in a future study.

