3 STUDY DESIGN

Objective 1: Culturally and linguistically adapt the STAR-VTF online training modules for Latino caregivers of PLWD

Findings from our stakeholder interviews indicate that no major changes to the intervention’s core components are required. Instead, we need to improve the content and

language used in the online training modules. The first adaptation will be to expand the content in the “Overview of Dementia” section of module 1. The content will address common beliefs and attitudes about dementia that result in families normalizing dementia symptoms and stigmatizing PLWD. The second adaptation will be to revise the language across all modules. We will eliminate any language that stakeholders suggested could be stigmatizing, offensive, and culturally irrelevant. We will rewrite the content to a 6th grade or lower reading level – a suggestion made by frontline clinician and health educator stakeholders. The content of the modules will be translated and the voiceover presentations recorded in Spanish. The third adaptation will be to incorporate content into module 7 that reflects the structure of Latino families (e.g., tendency to live multigenerational households) and how caregiving can often be a shared responsibility within the family unit.

The PI will lead this adaptation work with support from the study’s staff member. Feedback on draft adaptations will be obtained from stakeholders, including Latino caregivers of PLWD and Spanish-English bilingual and bicultural health educators. These individuals are members of a community advisory board. We will refine adaptations based on stakeholder feedback.

Objective 2: Pilot test Latino caregivers’ responses to the adapted online training modules

The study will use a single-arm pilot trial design. Participants will be up to 20 caregivers of PLWD. We will target individuals who are: aged 18 years or older, live with PLWD or within 5 miles, provide at least 8 hours of care per week, provide care to PLWD who lives at home, and self-identify as Hispanic/Latino.

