4 SELECTION AND ENROLLMENT OF PARTICIPANTS

4.1 Inclusion Criteria

Participants will be eligible if they meet the following criteria:

- Age 18 years or older
- Live with PLWD or within 5 miles
- Provide at least 8 hours of care per week
- Self-identify as Hispanic/Latino
- Caregiver self-report of PLWD having ≥ 3 BPSD occurring ≥ 3 in past week

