
What language do you prefer to speak? * must provide value
	
  English  Spanish  Other 

What language(s) do you speak at home? * must provide value
	
  English  Spanish  Other 

Are you of Hispanic, Latino/a, or Spanish origin? * must provide value
	
  No, not of Hispanic, Latino/a, or Spanish origin  Yes 
 
reset

What is your race? * must provide value
	
  White  Black or African American  American Indian or Alaska Native  Asian Indian  Chinese  Filipino  Japanese  Korean  Vietnamese  Other Asian  Native Hawaiian  Guamanian or Chamorro  Samoan  Other Pacific Islander  Other, specify 
 
One or more categories may be selected.

What is your gender? * must provide value
	
  Female  Male  Other 
 
reset

Thinking about members of your family that live in your household, what is the combined annual income, meaning the total pre-tax income from all sources earned in the past year?

* must provide value

- \$0 to \$9,999
- \$10,000 to \$14,999
- \$15,000 to \$19,999
- \$20,000 to \$34,999
- \$35,000 to \$49,999
- \$50,000 to \$74,999
- \$75,000 to \$99,999
- \$100,000 to \$199,999
- \$200,000 or more
- don't want to disclose

[reset](#)

Do you own a smartphone, tablet, laptop or computer?

* must provide value

- Smartphone
- Tablet
- Laptop
- Computer
- None

Do you or any member of your household have access to the Internet using a:

- cellular data plan for a smartphone or other mobile device?
- broadband (high speed) Internet service such as cable, fiber optic, or DSL service installed in this household?
- satellite Internet service installed in this household?
- dial-up Internet service installed in this household?
- some other service?

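### Section 9.5 declines subgroup analyses and no summary by language version is planned, so the quantitative results could mask a poorly performing Spanish version, mainly if Spanish users are a minority

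*Combined protocol and SAP*

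**What the plan says.** Objective 1 (Section 1.2) is to "culturally and linguistically adapt the STAR-VTF online training modules for Latino caregivers of PLWD". Section 3 adds, under that objective: "The content of the modules will be translated and the voiceover presentations recorded in Spanish". According to the Précis (Interventions and Duration), each caregiver receives the modules in whichever of English or Spanish they prefer. Section 3, Objective 2, says the same of the workbook. Section 3, Objective 3, puts English and Spanish versions of both primary instruments into the REDCap survey. It says nothing about the language of the System Usability Scale.

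Both languages share one small arm. Section 9.2 reads: "We have selected a sample size of up to 20 caregivers for study participation for pragmatic reasons". The related eligibility criterion in Section 4.1 is "Self-identify as Hispanic/Latino", which concerns ethnicity and not language. Sections 4.1 to 4.3 and 9.2 set no language quota or minimum. The accrual rule in Section 9.3 ("If we are unable to recruit at least 5 study participants during that 4-month period") counts everyone together.

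Section 9.1 says the study was not designed to test hypotheses. Section 9.5 plans descriptive statistics for quantitative outcomes and qualitative procedures for the interviews, then closes: "Given the small sample size and study objectives, we will not perform subgroup analyses". No section plans a description of any outcome by language version.

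**The concern.** The pilot is meant to ready the modules and the survey for a later study (Section 9.1). For that purpose, one of the first things to know is whether caregivers who use the Spanish modules complete them and find them usable. Overall figures from a single arm do not answer this, because good results from English users can offset poor ones from Spanish users.

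The two reasons given in Section 9.5 do not fit a descriptive table. A small sample is a sound reason not to test subgroups, but nothing in this study is tested, so a table with counts needs no power. The study objectives point the other way, since linguistic adaptation is one of them. At stake is a later study that takes forward a Spanish version whose weaknesses did not show in the reported figures.

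**Working it through.** **1. The plan's own figure.** There is none to reproduce. The maximum of 20 is pragmatic, and the documents give no expected scores, completion rates or language mix. All scores, rates and shares below are assumptions.

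**2. Dilution.** With nS Spanish users and nE = 20 − nS English users, the overall figure is the weighted mean (nE × E + nS × S) / 20. Assume mean usability of E = 80 and S = 50 (the documents give no total-score range, so 0 to 100 is assumed), and module completion of 90% and 40%.

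| Spanish users of 20 | Overall usability | Overall completion |
|---|---|---|
| 4 | (16 × 80 + 4 × 50)/20 = 74 | (16 × 0.90 + 4 × 0.40)/20 = 80% |
| 6 | (14 × 80 + 6 × 50)/20 = 71 | (14 × 0.90 + 6 × 0.40)/20 = 75% |
| 10 | (10 × 80 + 10 × 50)/20 = 65 | (10 × 0.90 + 10 × 0.40)/20 = 65% |
| 14 | (6 × 80 + 14 × 50)/20 = 59 | (6 × 0.90 + 14 × 0.40)/20 = 55% |
| 16 | (4 × 80 + 16 × 50)/20 = 56 | (4 × 0.90 + 16 × 0.40)/20 = 50% |

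With 4 Spanish users the overall mean lies 6 points from the English figure and 24 from the Spanish one. With 16 it is the reverse. Masking is therefore strong when Spanish users are a minority and weak when they are the majority.

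**3. Language mix.** No quota exists, so suppose each enrolled caregiver uses Spanish independently with probability p. The binomial chance of 3 or fewer Spanish users among 20 is 41% for p = 0.2, 11% for p = 0.3 and about 0.1% for p = 0.5. At the floor of 5 participants, the chance of no Spanish user, (1 − p)^5, is 33%, 17% and 3% for the same shares. Without counts by version, a reader could not tell which of these situations arose.

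**4. What a split would show.** With 10 users of each version, 9 English completers and 4 Spanish completers, the table reads 90% and 40%, where the overall figure is 13/20 = 65%. The exact (Clopper-Pearson) 95% interval for 4/10 is 12% to 74%. That is useful as description and too imprecise for inference.

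**The case against.** Several counter-arguments have force.

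- **Wording.** A reader might infer that Section 9.5 forbids every breakdown. It does not say so. It declines subgroup analyses, a term it leaves undefined, in a study without hypothesis tests. A by-language table is unplanned, and not clearly prohibited. This stands, but the plan as written still produces no such table.
- **Interviews.** A reader might infer that a failing Spanish version would go unnoticed. Exit interviews (Sections 3, 6.2.4 and 9.4.2) ask about the modules and the survey, and with at most 20 people a language problem could well emerge. This stands. However, language is not a named theme, and interviews do not supply completion or usability by version.
- **Advisory board.** Objective 1 is development work, checked by feedback from a community advisory board (Section 3), and the English text is revised too. True, but the board comments on draft adaptations and not on pilot use, and Spanish is the only new language.
- **Language mix and spread.** Recruitment includes Spanish-language media and federally qualified health centers (Section 4.3), so a Spanish majority is possible, and masking is then weak. A standard deviation would also hint at a split: with 6 users at 50 and 14 at 80 it is 30 × √(0.3 × 0.7) ≈ 14 even with no spread within groups. Both points stand, but a wide spread does not say which version caused it.
- **Causation.** A split would not isolate translation quality. Language is self-chosen, and differences may reflect education, devices or Internet access. This stands and limits the table to description.
- **Data capture.** A reader might infer that the version received is unknowable because the questionnaire item ("What language do you prefer to speak") allows several answers. The documents do not present that item as the delivery record, and staff must settle on one language to mail the workbook. What remains is that no section describes a field that stores the version delivered.

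**Conclusion.** The concern holds for the quantitative summaries. Two language versions are piloted in one small arm, linguistic adaptation is an objective, and nothing in the plan describes results by version. Reading Section 9.5 as producing overall summaries only is an inference from a single arm, descriptive statistics and no subgroup analyses, but it is the natural one.

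The size depends on a language mix that the documents do not give. On the assumed scores, a Spanish mean of 50 appears as 74 or 71 overall when Spanish users are 4 or 6 of 20, and as 59 or 56 when they are 14 or 16. The documents do not support the stronger claims that a Spanish failure must be hidden, or that a by-language table would show whether the translation works. Declining subgroup tests at this sample size is right. The gap is the missing description.

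**What to change.** Replace the last sentence of Section 9.5 with wording such as: *No subgroup hypothesis tests or inferences will be made. Module completion, System Usability Scale scores, the two primary outcome scales and REDCap survey completion will also be described by language version received (English/Spanish), with counts.* Survey completion is not among the outcomes in Section 9.4, but it serves Objective 3.

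Record the version delivered as a single-choice field, held under the study identification number. The questionnaire item asks about the language preferred for speaking and permits several answers, so it cannot be relied on for this. Section 10.2 has identifying data destroyed once recruitment ends, which is a further reason to store the version with the study data from the start.

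The cost is one descriptive table and one field, with no change to design, sample size or participant burden. The small downside is that cells will be small and imprecise. The report should state that differences are descriptive and cannot be attributed to the translation alone.
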